The study sample consisted of 120 patients aged between 18 and 65 years old, who ranked 4 (less urgent) and 5 (non-urgent) based on Canadian Emergency Department Triage and who had no visual, audial, or lingual disabilities, and no mental disorder. Only those patients who planned to have PIC insertion and were suitable for having PIC insertion at their antecubital location using 20 Gauge (pink) cannula were eligible. Patients who applied to the emergency service for acute pain and had not used analgesics within 24 hours before applying to the emergency service or had previously experienced multiple PIC procedures, were excluded from the research scope. Patients who refused to participate in the study, who were not eligible for 20 G PIC insertion, who were not in the age range of 18-65 years, and who could not be inserted PIC at the first time (n=98) were excluded from the study (Figure 1). The CONSORT checklist was followed in reporting this study.

4. Sample Size Calculation

The sample size was estimated by using the Medicres E-piccos program (<https://www.e-piccos.com/apps/power/sscm>), and it was determined that a minimum of 117 patients were

needed [d (effect size/ effect width) =1.60, α =0.05, β =0.10, and power=0.95]. The study sample numbered 120 patients.

5. Randomisation

The randomisation method was used by layering according to gender. The patients were distributed into groups using the Medicres E-piccos randomisation program (<https://www.e-piccos.com/apps/calculation/rapg>). Three groups of 40 patients each were generated, and 120 patients were randomised into the control or experimental groups.

6. Data Collection Tools

The data were collected in the study scope by means of a data collection form consisting of the socio-demographic characteristics of the patients and the visual analog scale (VAS). VAS was used to evaluate pain caused by needle insertion. In the VAS of 10 cm length, “0” indicated no pain, and “10” indicated the severest pain. The scale between 1 and 10 was used to evaluate levels of satisfaction with the procedure. In this scale, “1” indicated the level of least satisfaction and “10” indicated the highest satisfaction level. The patients marked their pain and satisfaction levels on this scale.

7. PIC Insertion Procedure

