The patient was seated in a position that suited the procedure. The arms were positioned below the heart level, when possible. An area in the antecubital location with no skin lesion was selected for PIC. The antecubital area and back of the hand are mostly preferred for the PIC. Because the antecubital vein, which is more commonly used in the PIC applications, has been reported to be less painful than the veins in the back of the hand in the literature, the PICs were all applied to the antecubital vein in the left arm. An autoguard shielded PEU-Vialon (BD-Venflon, Becton Dickinson) was used as an PIC. Lateral holding sections of the cannula were positioned horizontally. The tourniquet was attached to the patient’s outfit at 5-12 cm above the selected vein. The patient was asked to open and close his/her hand and

make a fist. The veins in the arm used for application were monitored and palpated. The selected location was cleaned by antiseptic solution and 1-2 minutes were allowed for drying. The PIC was held as the blade of the needle was facing upward. A location approximately 3-5 cm below the point of insertion was pressed near the thumb of the empty hand to stabilize the vein, and the skin was stretched downwards. When the needle was inserted into the vein, the plastic portion was gently pushed through the inside of the vein. The tourniquet was undone and the catheter was fixed on the skin with a plaster. This application was completed within approximately 2-3 minutes. All of the PIC insertion procedures were performed by the same researcher. The other researcher, who did not know which patient was in which group, collected the data on the assessment of PIC procedure-associated pain and satisfaction levels immediately after PIC insertion using face-to-face interviews.

8. Ethical Consideration

A permit (number 18/7 and dated 10/16/2018) from the Ethical Committee of the hospital where the research was conducted was received, and the hospital's written permission was obtained. Moreover, the procedures to be carried out were explained to the patients prior to the procedure, and their written and oral consents were received.

9. Data Analysis

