The collected data were analyzed by using the SPSS 21.0 package program. The variables determined by counting were shown in numbers and percentages, and the variables determined by measurements were shown as averages and standard deviations. T test and One way ANOVA were used in comparative statistics. A $p < 0.05$ level was accepted as an indication of significant difference in statistical decisions.

Figure-1. Diagram showing the flow of participants.

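### Pain is marked once, after insertion, and compared without adjustment; a pre-procedure mark used in ANCOVA would gain precision, though the group contrast is unbiased without it

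*Protocol*

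**What the plan says.** - **What is recorded.** Protocol section 6 describes a "data collection form consisting of the socio-demographic characteristics of the patients and the visual analog scale (VAS"), plus a 1-to-10 satisfaction scale. It lists no pre-procedure pain mark and no item on presenting pain or analgesic use.
- **What the scale targets.** Section 6: "VAS was used to evaluate pain caused by needle insertion".
- **When.** Section 7 has a second researcher, unaware of the group, collect "pain and satisfaction levels immediately after PIC insertion using face-to-face interviews". No other time point is described.
- **Who.** Section 3 takes emergency patients "ranked 4 (less urgent) and 5 (non-urgent) based on Canadian Emergency Department Triage" and excludes "Patients who applied to the emergency service for acute pain and had not used analgesics within 24 hours before applying to the emergency service".
- **Allocation.** Section 5 stratifies by gender and forms three groups of 40.
- **Analysis.** Section 9: "T test and One way ANOVA were used in comparative statistics". No covariate is named, and the stratification factor does not appear.

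**The concern.** The patients come from an emergency unit. Triage levels 4 and 5 limit urgency, which is not the same as limiting pain. The exclusion joins acute pain and absence of analgesics with "and". Read literally, a patient with acute pain who had taken an analgesic stays eligible, and so does a patient without acute pain whatever they had taken. Presenting pain and analgesia can therefore differ between patients and may colour a single rating made just after the needle.

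If they do, that variation sits in the error term of the t test and ANOVA. A separate analysis plan could add sex as a covariate, but it could not adjust for a pain value that was never collected. What is at stake is the width of the confidence interval for the distraction effect, and hence power at 40 per group.

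**Working it through.** **Inputs from the protocol.** 40 per group; α = 0.05 (taken as two-sided); effect 1.60 (section 4, without saying whether it is standardised or in VAS points); minimum total 117, which is 39 per group.

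**Inputs that are assumptions.** The outcome SD, the baseline–outcome correlation r, and a smaller difference of 1.2 points used as a second scenario.

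**1. The protocol's own figure, used to choose an SD.** Normal approximation: n per group = 2(z₁₋α/₂ + z₁₋β)² / d².
- With 1.60 as a standardised effect: 2(1.960 + 1.282)²/1.60² = 8.2, so 9 per group (27 in total) at 90% power; 2(1.960 + 1.645)²/1.60² = 10.2, so 11 per group (33 in total) at 95%. Neither gives 117.
- With 1.60 as a raw VAS difference, 39 per group implies SD = 1.60 / [(z₁₋α/₂ + z₁₋β)√(2/39)], which is 2.18 at 90% power and 1.96 at 95%.

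The SD of 2.15 used below lies inside that 1.96–2.18 interval. It remains an assumption.

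**2. Does the missing baseline bias the comparison?** In 20,000 simulated trials with no true effect, two groups of 40 and r = 0.5 between existing pain and the rating, the unadjusted t test rejected in 4.9% and the mean difference was about 0 (−0.001 SD). Validity is intact.

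**3. Precision gained by adjustment.** Residual variance is multiplied by 1 − r², so 40 per group is worth 40/(1 − r²). Pairwise power is from the two-sided two-sample noncentral t at 40 per group, with residual SD 2.15√(1 − r²). The unadjusted standard error is 2.15√(2/40) = 0.481.

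| r | 1 − r² | 40 per group is worth | Power, 1.6 points | Power, 1.2 points |
|---|---|---|---|---|
| 0 (unadjusted) | 1.00 | 40.0 | 90.8% | 69.3% |
| 0.1 | 0.99 | 40.4 | 91.0% | 69.8% |
| 0.2 | 0.96 | 41.7 | 91.8% | 71.1% |
| 0.3 | 0.91 | 44.0 | 93.1% | 73.4% |
| 0.5 | 0.75 | 53.3 | 96.7% | 81.2% |
| 0.6 | 0.64 | 62.5 | 98.4% | 86.9% |

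**4. Sensitivity to the SD.** For a raw 1.6-point difference (normal approximation), unadjusted → r = 0.3 → r = 0.5:
- SD 2.0: 94.7% → 96.3% → 98.5%
- SD 2.5: 81.7% → 85.1% → 91.1%
- SD 3.0: 66.5% → 70.6% → 78.6%

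**5. Chance imbalance.** The difference in mean baseline pain between two groups of 40 has standard error √(2/40) = 0.224 SD, so a 95% range of ±1.96 × 0.224 = ±0.44 SD on the baseline scale. Only r times this reaches the outcome: 0.3 × 0.44 = 0.13 SD to 0.6 × 0.44 = 0.26 SD. That variation is already inside the unadjusted standard error. It is the loss in step 3 seen from another side and should not be counted again.

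**6. Why not a change score.** With equal variances, post minus pre has variance 2(1 − r) relative to the post value alone: 1.4 at r = 0.3, 1.0 at r = 0.5, 0.8 at r = 0.6. Below r = 0.5 it is worse than no adjustment, and at 0.6 it still does less well than ANCOVA (0.64).

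**The case against.** A reader might infer that needle pain cannot be told apart from existing pain, so that the trial fails to answer its question. The documents do not support that. The hypotheses in section 1 compare the distraction methods with control, allocation is randomised, and the scale is directed at needle pain. Existing pain may blur an individual score or the absolute level of pain in a group, but it does not bias the contrast.

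Three further objections have weight.
- **r may be low.** Presenting pain of any cause and a needle stick at the elbow are different pains, and the eligibility rules remove some existing pain. At r = 0.1 to 0.2 the variance falls by only 1% to 4%. This stands, and is why the range starts at 0.1.
- **The premise leans on a poorly worded exclusion.** If the sentence was meant to remove both acute pain and recent analgesic use, there would be less baseline variation to explain. This also stands; the wording does not settle which was meant.
- **Covariates are commonly left to the analysis plan.** That is fair for the choice of model, including adjustment for sex. It does not cover the pre-procedure mark, which depends on the data collection that the protocol fixes.

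Finally, asking for a pain rating just before a distraction intervention may direct attention to pain. An equal effect in all groups is plausible but not established, so this counts as a real, if small, cost.

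**Conclusion.** The point holds as an optional improvement in precision. With no baseline pain described and none of the named tests adjusted, the plan forgoes a variance reduction of 1% to 36% for r between 0.1 and 0.6. At SD 2.15 and 40 per group, pairwise power is 91% unadjusted and 91–98% adjusted for a raw 1.6-point difference; for 1.2 points it is 69% and 70–87%. The gain is negligible at r of 0.1 to 0.2 and becomes material from about 0.4 to 0.5 (16% to 25% of variance).

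The SD, the 1.2-point difference and r are all assumed, and reading 1.60 as raw VAS points is an interpretation. The larger gains, such as 69% to 87%, need both the smaller difference and r = 0.6, so they should not be quoted as the expected benefit.

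**What to change.** - **Analysis.** Replace the unadjusted comparison of pain with ANCOVA of post-insertion VAS on group and sex (the stratification factor), adding pre-procedure VAS as a covariate. Do not analyse change from baseline.
- **Data.** Add one pre-procedure mark on the same 10 cm scale, taken before the patient learns the group, and record analgesic use in the last 24 hours on the existing form.
- **Eligibility wording.** Clarify the sentence on acute pain and analgesic use so that it says which combinations are excluded, and reconcile it with who was enrolled.

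The cost is one scale mark, one form item and an extra covariate, with no change in trial size. The downside is the possible drawing of attention to pain before the intervention.

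The protocol describes the trial as already conducted. For the data in hand, the analysis can adjust for sex and use any presenting-pain information that was recorded; otherwise the missing baseline should be reported as a limitation on precision, and the extra mark kept for a repeat study.
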